10.5.2 Safety Analyses

Summaries of safety data for subjects in Cohort 2 will be presented by treatment – ZX008 at assigned dose or placebo – separately for the Titration, Maintenance and T + M periods. The number and percentage of subjects in each treatment group with AEs will be displayed by body system and preferred term using the Medical Dictionary for Regulatory Activities (MedDRA). Summaries of AEs by severity and relationship to study drug will also be presented. A separate summary will be provided for all SAEs. Selected summaries will be repeated broken out by age group, ie, for ages < 6 years and ≥ 6 years.

Hematology and chemistry laboratory results for subjects in Cohort 2 will be summarized by descriptive statistics at each time point available. Mean change from baseline will also be calculated for continuous hematology and chemistry results at all time points available.

Laboratory tests, vital signs, physical examinations, neurological examinations, ECG, Doppler ECHO, C-SSRS, Tanner Staging results, etc, will be summarized appropriately, by treatment. All safety summaries for subjects in Cohort 2 will be based on the SAF Population.

For subjects in Cohort 1, safety will be summarized by treatment regimen and by treatment period, either the PK Evaluation or Transition Period. Summaries will also be produced for all subjects in Cohort 1 combined regardless of regimen. AEs, laboratory results, vital signs and other endpoints will be described using similar statistics as those used for Cohort 2.

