5.1.5 Safety Population

All safety analyses will be performed on the SAF Population defined as all randomized subjects who receive at least one dose of ZX008 or placebo. Subjects will be analyzed according to the treatment group to which they were randomized.

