6.1.6 Visit Windows

The following rules will be used to window data into treatment periods tabulations. For all by-visit tabulations, the nominal visit as recorded on the CRF will be used.

Double Blind Treatment Period	The Double-Blind Treatment Period start date is the date of first dose. The Double-Blind Treatment Period end date is the last date the patient was on study treatment. The Double-Blind Treatment Period includes time from first
-------------------------------	---

	treatment start date, which includes 21 days of Titration period, 12 weeks of Maintenance period and Taper/Transition period (14 days) - For subjects who discontinue early from the study, the double-blind treatment period end date will be the date at the early termination visit (Visit 12).
Titration Period	The Titration Period covers up to the first 21 days of treatment while subjects are titrated to their randomized dose. It begins on the first day of treatment (Study Day 1) and extends through Visit 6 (when the patient has reached their randomization dose). The Titration Period applies to all subjects including placebo recipients. If a subject withdraws from the study prior to treatment in the maintenance period, all safety assessments and events up to and including the date of study withdrawal will be tabulated in the titration period.
Maintenance Period	The Maintenance Period covers the 12 weeks following the end of the titration period. It begins on the date of Visit 6 + 1 day and extends through the end of study/early termination visit (Visit 12).
Titration +Maintenance Period (T+M)	The T+M period combines the Titration and Maintenance periods, beginning on the date of first treatment (Study Day 1) and extending to the end of the 12 week Maintenance Period. The primary efficacy endpoint is calculated based on data from the T+M period.
Taper/Transition Period	The Taper/Transition period consists of approximate 14- days starting from end of study/early termination visit (Visit 12) + 1 day. For patients who are not entering into the open-label extension study, patients will gradually be tapered off of study medication. Patients entering the open-label extension study will first enter the transition phase where all patients will be on a dose of 0.2mg/kg/day at the end of this phase. The end date of this period is considered to be the date recorded at Visit 13.

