6.2.4 Treatment Exposure and Compliance

6.2.4.1 *Treatment Exposure*

Exposure will be summarized for the safety population.

Duration of exposure to treatment (i.e., time on treatment in days) will be calculated per subject as the number of days with IMP intake during the study and will be summarized using descriptive statistics (mean, standard deviation, median, and range) for the safety population. The per subject duration of exposure will be calculated as follows:

Date of last IMP administration – Date of first IMP intake + 1

The duration of exposure summary statistics will be presented by treatment group for the combined Titration, Maintenance and Taper/Transition periods. Also, the exposure subject data listing will be presented.

6.2.4.2 *Compliance*

Compliance will be summarized for the SAF and mITT.

Study medication is to be administered twice daily, and compliance is recorded in the eDiary as full (both doses), partial (less than full daily dose) or missed (both doses) each day. From this, compliance will be calculated by assuming that a missed dose=0% of dose consumed, partial=50% of dose consumed, and full=100% of dose consumed. For each subject, a daily compliance score will be thus obtained.

Compliance will be summarized for the SAF population over the course of T+M and Maintenance only, reported by treatment group.

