6.4.1 Adverse Events

An AE is defined as any unfavorable and unintended sign (including an abnormal, clinically significant laboratory finding), symptom, or disease temporally associated with the use of a medicinal (investigational) product, whether or not considered related to the medicinal (investigational) product. The period of observation for adverse events extends from the time the subject gives informed consent until the end of the titration/transition period (Visit 13). For patients who continue into the open-label extension study, AEs of special interest will continue to be monitored for up to 6 months after the last dose of study medication.

A TEAE is defined as any AE that based on start date information occurs after the first intake of study treatment. All other AEs occurring after enrollment and prior to the first administration of study treatment are defined as non-treatment emergent AEs (non-TEAEs).

Any missing relationship will be considered as “related.”

The severity of AEs (whether non-serious or serious AEs) will be assessed by the investigator as follows:

Severity Definition of Adverse Events:

Mild - A type of AE that is usually transient and may require only minimal treatment or therapeutic intervention. The event does not generally interfere with usual activities of daily living.

Moderate - A type of AE that is usually alleviated with additional specific therapeutic intervention. The event interferes with usual activities of daily living, causing discomfort but poses no significant or permanent risk of harm to the research participant.

Severe - A type of AE that interrupts usual activities of daily living, or significantly affects clinical status, or may require intensive therapeutic intervention.

Any missing severity will be imputed as “severe.”

The original terms used by the investigators in the eCRFs to identify AEs will be coded using the most recent version of the MedDRA implemented by the sponsor at the end of the study.

6.4.1.1 Overview of Events:

The number and percent of patients with at least one of the following events will be summarized in an overall summary table:

- TEAE.
- Serious TEAE
- Related TEAE
- Related serious TEAE.
- TEAE leading to treatment discontinuation
- Death

The percentage denominator for the calculation of percentage will be the number of subjects in the SAF.

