6.4.1.2 Treatment Emergent Adverse Events

The following summaries will display the number and percentage of subjects with adverse events by system organ class (SOC) and preferred term (sorted alphabetically) for each treatment group and overall:

- All TEAEs

- Serious TEAEs
- TEAEs by Maximum Severity
- Study Drug Related TEAEs
- All AEs that lead to premature discontinuation from the study

An additional summary will tally the number and percent of subjects in each treatment group who experience an AE that occurs in at least 5% of subjects. The summary will be presented by preferred term in decreasing order of incidence.

The summaries will be provided for the double-blind treatment period. No inferential statistical methods (i.e., methods that yield p-values) will be used to compare treatment groups on the frequency or severity of AEs.

Additionally, the following listings will be produced for all enrolled subjects:

- All AEs, events considered to be TEAE will be identified in the listing
- Serious AEs
- AEs that lead to premature discontinuation from the study
- Deaths

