6.9 CHANGES TO METHODS PLANNED IN THE PROTOCOL

- Protocol states that safety data will be summarized separately for the titration and maintenance periods as well as for the combined T+M period. Instead safety will be summarized only for the combined T+M..
- Protocol states that subjects in the safety population will be summarized by the treatment actually received. However, safety data will be presented by randomized treatment group except where noted otherwise.
- Protocol states that a sensitivity analysis for the primary efficacy endpoint will be conducted by adding a factor indicating whether a subject had a change in prescribed

dose or type of concomitant AED medication during the T+M Period, however this is not planned to be conducted.

- The protocol stated that the longest interval between convulsive seizures will be analyzed using a log-rank test. Instead groups will be compared with a Wilcoxon test.
- Responder analyses – The protocol included a $\geq 40\%$ response analysis as one of the key secondary endpoints. It was decided to not include this in the hierarchical testing of secondary endpoints.
- An analysis of the percentage of subjects who achieve a 25% reduction in seizures was added.,
- The Protocol states that the BRIEF rating scale will be used to evaluate cognition in children aged 2-18. The BRIEF-P will be used for children aged 2-4, and the BRIEF will evaluate children aged 5-18. The Protocol further states that the cognition subscale of the BRIEF will be used to evaluate cognition. The BRIEF and the BRIEF-P will be used to evaluate cognition.
- The Protocol states the Clinical Global Impression ratings by Investigator and Caregiver are exploratory endpoints. They are secondary endpoints.
- The protocol states the sample size is approximately 70 randomized subjects. As explained in [Section 6.1.10](#), the sample size was adjusted to approximately 80 randomized subjects based on data from the completed study of Epidiolex in Dravet syndrome.

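### The SAP's TEAE tables run through the transition period by randomised arm, so events that placebo children have on ZX008 count as placebo, although SAP 6.9 limits safety summaries to T+M

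*SAP*

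**What the plan says.** **TEAE window.** SAP 6.4.1.2 states: "The summaries will be provided for the double-blind treatment period". SAP 6.1.6 (Double Blind Treatment Period) says this period "includes 21 days of Titration period, 12 weeks of Maintenance period and Taper/Transition period (14 days". In SAP 6.4.1, "A TEAE is defined as any AE that based on start date information occurs after the first intake of study treatment". That definition has a start but no stop, and no reset at a child's first ZX008 dose.

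**Arm.** SAP 5.1.5: "Subjects will be analyzed according to the treatment group to which they were randomized". SAP 6.9 repeats this as a deliberate change from the protocol.

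**Treatment in the transition.** For children entering the extension, SAP 6.1.6 says that "all patients will be on a dose of 0.2mg/kg/day at the end of this phase". Protocol 5.5.7 (Table 7) keeps former-placebo children on placebo for transition Days 1-7 and gives ZX008 0.2 mg/kg/day on Days 8-14. SAP Table 4 and the text beneath it start ZX008 on transition Day 1.

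**Stated safety period.** SAP 6.9: "Instead safety will be summarized only for the combined T+M". Protocol 10.5.2 asks for safety summaries "separately for the Titration, Maintenance and T + M periods". Protocol 10.4.2 puts the time from the end of T+M to Visit 13 in a separate Follow-up Period.

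**Exposure.** SAP 6.2.4.1: "The duration of exposure summary statistics will be presented by treatment group for the combined Titration, Maintenance and Taper/Transition periods".

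**The concern.** Placebo is the only concurrent reference for ZX008 adverse events in this paediatric trial. If its column includes first-exposure days on ZX008, events caused by the drug can appear as placebo background. The related-TEAE table would carry the same error, and because the transition is blinded the sites cannot flag such events as arising on ZX008.

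There is also a problem of execution. A programmer following 6.9 would stop at Visit 12; one following 6.4.1.2 with 6.1.6 would run to the end of the transition. Both would be following the SAP, and their tables would differ. The table list in SAP Appendix 1 has no separate transition table for events or exposure, so the switch would be visible only in listings.

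**Working it through.** **1. Window length.** Titration 21 days + Maintenance 84 days = 105 days (15 weeks). Adding 14 days of taper/transition gives 119 days (17 weeks), which matches the double-blind duration of up to 17 weeks in the protocol synopsis.

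**2. Who is affected.** Only placebo children who complete T+M and enter the extension. Early discontinuers are not affected, because SAP 6.1.6 ends their window at the early termination visit. Placebo children who taper off are not affected, because Protocol Table 6 gives them placebo.

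**3. ZX008 days counted as placebo, per affected child.**

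| Schedule | ZX008 days | Share of 119 |
|---|---|---|
| Protocol Table 7 | 7 | 7/119 = 5.9% |
| SAP Table 4 and text | 14 | 14/119 = 11.8% |

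**4. Across the arm, protocol schedule.** Placebo arm n = 40 (SAP 6.1.10) or 45 (Protocol 10.1). The documents give no entry rate; assume 80-95%, so k = 0.80n to 0.95n children.
- Low: 40 × 0.80 × 7 = 224 subject-days. High: 45 × 0.95 × 7 = 299.
- Share of placebo-arm days = 7k/(105n + 14k) = 4.8% to 5.6%.

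**5. Illustration of the effect on incidence.** Every event rate here is an assumption. Take an AE with 5% incidence on placebo and 40% on ZX008 over T+M, with constant hazards h0 = -ln(0.95)/105 and h1 = -ln(0.60)/105 per day. Let c be the hazard at 0.2 mg/kg/day relative to h1, and e the share entering the extension (0.80-0.95). The rest stay at their T+M value and the taper is ignored.
- Placebo = e[1 - 0.95 exp(-7h0 - 7c·h1)] + (1 - e)0.05
- ZX008 = e[1 - 0.60 exp(-7h1 - 7c·h1)] + (1 - e)0.40

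| Case | Placebo | ZX008 | Risk ratio | Difference (points) |
|---|---|---|---|---|
| T+M only | 5.0% | 40.0% | 8.0 | 35.0 |
| To 119 days, c = 0.5 | 6.5-6.8% | 42.4-42.8% | 6.3-6.5 | 35.9-36.0 |
| To 119 days, c = 1 | 7.8-8.3% | 43.2-43.8% | 5.3-5.5 | 35.4 |

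If the placebo arm stayed on placebo for all 14 days, its incidence would be 5.5-5.6% and the risk ratio 7.6-7.8. Most of the fall is therefore misattribution and not the longer window.

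In head count, the chance of a first event in 7 ZX008 days is 1 - exp(-7h1) = 3.35%, or 1.69% at half hazard. Extra placebo subjects with the event = k × 0.95 × that chance = 1.0-1.4, or 0.5-0.7, on top of the 2.0-2.25 expected.

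With 20% incidence on ZX008, the risk ratio is 3.4-3.7 against 4.0, and the difference 15.5-15.7 points against 15.0.

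**The case against.** The strongest reply is that SAP 6.9 already states the intended T+M cut, so the contamination arises only if 6.9 is overlooked and 6.4.1.2 merely needs aligning. Other safety outputs support that intention: the C-SSRS summaries (6.4.10) use T+M, and the out-of-range laboratory listing (6.4.9) uses Baseline and T+M. It is fair to call this a drafting conflict. It still has to be resolved, because 6.4.1.2 is the section that specifies the TEAE tables and its period is explicitly defined in 6.1.6.

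The reply is also right that the size rests on assumed inputs. Entry rate, AE rates, constant hazard and the hazard at the lower dose are not in the documents, and even the 40% example moves only about 0.5-1.4 placebo subjects.

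Three stronger readings are tempting and not supported:
- *That Protocol 10.5.2 also says T+M only.* It asks for three sets of summaries: Titration, Maintenance and T+M. It names no later period, but the restriction to T+M alone is the SAP's own declared change.
- *That the exposure table breaches SAP 6.9 or Protocol 10.5.2.* Neither mentions exposure, and 6.2.4.1 sets its own window. Counting all days on study medication is ordinary practice. What remains is that a placebo child's 119 days would appear undivided when, on the protocol schedule, 112 were on placebo and 7 on ZX008.
- *That SAP Table 4 proves 14 days of ZX008.* The SAP introduces that table as hypothetical, and it conflicts with the protocol's dosing table. Seven days is the safer figure, though the text under Table 4 states Day 1 without qualification and needs correcting.

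**Conclusion.** The point holds for the TEAE tables. As written, SAP 6.4.1.2 with 6.1.6 counts events starting on ZX008 as placebo events and contradicts SAP 6.9. The misattributed time is 7 of 119 days per placebo child entering the extension under the protocol schedule, or 14 under the SAP's. Under the assumed 80-95% entry and the protocol schedule, about 5% of placebo-arm days are affected.

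The direction is towards a smaller risk ratio for drug-related events; the amount is illustrative only. The risk difference need not shrink, because the ZX008 arm's window is extended too, and on the protocol schedule it did not shrink in the cases worked. A reader might infer that the trial's formal conclusions are at risk. They are not: SAP 6.4.1.2 plans no p-values for AEs, and the primary and key secondary efficacy analyses over T+M do not use transition data.

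The exposure table has a separate and lesser fault of labelling. Both should be corrected before unblinding.

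**What to change.** - Amend SAP 6.4.1.2 so that the between-arm TEAE tables end at the end of T+M (Visit 12), in line with 6.9.
- Add one Taper/Transition table of AEs and exposure by treatment actually taken (placebo or ZX008), so that events after Visit 12 remain visible in both arms.
- For former-placebo children, start ZX008 at the scheduled Step 2 date, transition Day 8 (Visit 12 + 8 days, since SAP 6.1.6 starts the period at Visit 12 + 1 day), unless an actual start date is recorded. Protocol 5.5.2 records when bottles are assigned, and no section specifies recording when the Step 2 bottle is started.
- Split the exposure summary in 6.2.4.1 into T+M and Taper/Transition.
- Align SAP Table 4 and its text with Protocol Table 7.

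The cost is a few lines of SAP text, one table cut-off, a split exposure table and one extra table. AE dates and treatment assignment are already collected, and nothing changes for patients.

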7. Clinically significant worsening of seizures, judged by investigator or subject/caregiver such that treatment outside of the protocol and other than ZX008 is assumed to be in the subject's best interest. Frequent or increased use of rescue medication may be considered indicative of worsening.
8. An "actual suicide attempt" as classified by the Columbia-Suicide Severity Rating Scale (C-SSRS).
9. It is the investigator's opinion that it is not in the subject's best interest to continue in the study.
10. Subject is found to be pregnant while on study.

Discontinuation decisions will be made at each participating site by the site investigator, except that discontinuations due to development of cardiovascular or cardiopulmonary complications are to be made by the IDSMC with input from the IPCAB and the investigator.

If feasible, the process of discontinuation should be discussed with the Medical Monitor. The decisions regarding the discontinuation of the investigational therapy, whether the study medication should be stopped immediately or tapered should be discussed with the Medical Monitor, but final decisions about the process will remain at the discretion of the site principal investigator.

Subjects who are discontinued from the clinical investigation (Cohort 2) for any reason will not be replaced.

Subjects may withdraw their consent to participate in the study at any time without having to justify the reason for doing so. The decision to withdraw consent and discontinue participation in the study will not prejudice the subject's future medical treatment in any way. Subjects must be discontinued from receiving ZX008 and/or participating in any further study procedures under the following circumstances:

- The subject or the subject's legally authorized representative wishes to discontinue participation in the study.
- The investigator advises that the subject's safety or well-being could be compromised by further participation in the study.
- The Sponsor requests that a subject discontinues participation in the study (eg, due to suspicion of fraud, multiple enrollments in clinical studies, lack of compliance, etc).

The IDSMC may request that the study be terminated after review of the safety information at any time during the study. The IDSMC will review the data for the development of heart valve disease and pulmonary hypertension as they occur on a case-by-case basis and at regular meetings.

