5.5.5 Cohort 2: Taper Period

Subjects who complete all of the Maintenance Period and will not be continuing into the open-label extension trial, and subjects who discontinue from the study early, will be tapered off of study medication over 8 days and will receive no study drug during the final 6 days of the taper period. Study drug administration will not be resumed after completion of the taper period. The taper algorithm is shown in [Table 6](#).

Table 6. Taper Algorithm

Randomized Dose	Taper Step 1 Days 1-4 after study completion or early termination	Taper Step 2 Days 5-8 after study completion or early termination	Taper Step 3 Days 9-14 after study completion or early termination
ZX008 0.5 mg/kg/day	ZX008 0.4 mg/kg/day	ZX008 0.2 mg/kg/day	No study drug administration
Placebo	Placebo	Placebo	No study drug administration

Note: maximum daily dose of ZX008 is 20 mg

Study medication will continue to be administered as equal doses BID in the morning and in the evening approximately 12 hours apart, with food. Each dose should be separated by a minimum of 8 hours and a maximum of 12 hours. A missed dose of study medication may be taken later up to 8 hours before the next scheduled dose; otherwise, the missed dose should not be given. IMP will be administered using the oral dosing syringe provided.

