Subjects who complete all of the Maintenance Period and will not be continuing into the open-label extension study, and subjects who discontinue from the study early, will be tapered off of study medication. Study medication will continue to be administered as equal doses BID in the morning and in the evening approximately 12 hours apart, with food. Each dose should be separated by a minimum of 8 hours and a maximum of 12 hours. A missed dose of study medication may be taken later up to 8 hours before the next scheduled dose; otherwise, the missed dose should not be given. IMP will be administered using the oral dosing syringe provided.

The taper algorithm is indicated below.

Table 3. Taper Algorithm

Randomized Dose	Taper Step 1 Day 1-4 after study completion or early termination	Taper Step 2 Days 5-8 after study completion or early termination	Taper Step 3 Days 9-14 after study completion or early termination
ZX008 0.5 mg/kg/day	ZX008 0.4 mg/kg/day	ZX008 0.2 mg/kg/day	No study drug administration
Placebo	Placebo	Placebo	No study drug administration

Note: maximum daily dose of ZX008 is 20 mg.

Transition Period:

Subjects who complete the Maintenance Period and will be continuing into the open-label extension study will be transitioned from double-blind study medication to open-label ZX008 (hypothetical transition is depicted in [Table 4](#)). Study medication will be administered as equal doses BID in the morning and in the evening approximately 12 hours apart, with food. Each dose should be separated by a minimum of 8 hours and a maximum of 12 hours. A missed dose of study medication may be taken later up to 8 hours before the next scheduled dose; otherwise, the missed dose should not be given. Study medication will be administered using the oral dosing syringe provided.

All subjects entering the open-label extension study will be transitioned from their blinded daily dose (placebo, or assigned dose of ZX008) to the 0.2 mg/kg dose during the interval between Visits 12 and 13, without breaking the blind. The IVR/IWR system will assign two bottles of IMP to the subject, one for each step in the transition. A new bottle of IMP will be started by the subject at each level of the transition step.

Table 4. Transition Algorithm

Randomized Dose Selected for Cohort 2	Step 1 Days 1-7 after study completion	Step 2 Days 8-14 after study completion
--	---	--

ZX008 0.5 mg/kg/day	ZX008 0.4 mg/kg/day	ZX008 0.2 mg/kg/day

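### SAP 6.1.6 gives conflicting end dates for the double-blind treatment period, so adverse events during taper may be left out of the by-arm tables, for early discontinuers only or for everyone

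*SAP*

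**What the plan says.** SAP 6.1.6 (Visit Windows) defines the Double-Blind Treatment Period in one table cell that holds three statements about when the period ends:

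- A general rule: "The Double-Blind Treatment Period end date is the last date the patient was on study treatment".
- A list of contents: 21 days of titration, 12 weeks of maintenance and the 14-day Taper/Transition.
- A clause for one group: "For subjects who discontinue early from the study, the double-blind treatment period end date will be the date at the early termination visit", that is, Visit 12.

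SAP 6.4.1.2 attaches the by-arm tables (all, serious, by maximum severity, and related treatment-emergent events, by system organ class and preferred term) to this period: "The summaries will be provided for the double-blind treatment period".

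On what happens after the early termination visit, Protocol 5.5.5 states that completers not entering the extension and early discontinuers "will be tapered off of study medication over 8 days and will receive no study drug during the final 6 days of the taper period". SAP 3.2.2 and its Table 3 repeat the taper for early discontinuers. Protocol 4.5 allows an exception: "whether the study medication should be stopped immediately or tapered should be discussed with the Medical Monitor", with the site investigator deciding.

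Four other SAP provisions bear on the point:

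- SAP 6.4.1 observes adverse events to Visit 13 and calls any event with onset after first intake treatment-emergent, with no upper limit.
- SAP 6.1.6 starts the Taper/Transition period the day after Visit 12, whether that visit is end of study or early termination.
- SAP 6.2.4.1 counts exposure from first to last dose and presents it for Titration, Maintenance and Taper/Transition combined.
- SAP 6.9 lists, as a change from the protocol, that safety will be summarised for the combined T+M period only.

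**The concern.** Adverse events in early discontinuers during taper are collected, meet the definition of treatment-emergent, and occur on days that the SAP counts as exposure. Read literally, the early termination clause still removes them from the tables by system organ class and preferred term, while the same event in a completer who tapers is tabulated. The window then depends on completion status, which is known only after randomisation and may itself reflect tolerability: Protocol 4.5 lists an adverse event and worsening seizures among the reasons for discontinuation.

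What is at stake is whether the main by-arm safety tables cover the time during which subjects were dosed, and whether two programmers working from this SAP would produce the same tables.

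**Working it through.** No power or sample-size figure enters here. The check is day arithmetic, followed by a comparison of the readings that the SAP allows. On-medication days below means days on ZX008 or placebo.

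**Reproducing the schedule.** T+M = 21 + 12 × 7 = 105 days, so Visit 12 falls on Day 106 and Visit 13 on 106 + 14 = Day 120, as in the schedules of assessments. The taper has two 4-day steps, 4 + 4 = 8 days on medication, then Days 9-14, which is 6 days off: 8 + 6 = 14. This matches Protocol Table 6 and SAP Table 3. For a discontinuer, Protocol 6.2.5.11 puts Visit 13 at 14 days after discontinuation.

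**The readings side by side.**

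| Governing text | Completer who tapers: taper events in the tables? | Discontinuer who tapers: taper events in the tables? |
|---|---|---|
| SAP 6.1.6 early termination clause with 6.4.1.2 | Yes (105 + 14 = 119 days, or 105 + 8 = 113 to last dose) | No |
| SAP 6.1.6 last-day-on-treatment rule with 6.4.1.2 | Yes, through the 8 on-medication days | Yes, through the 8 on-medication days |
| SAP 6.9, T+M only | No | No |

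The general rule would keep these events. The early termination clause is the more specific sentence, so it is the natural one to program for discontinuers. Two of the three readings leave their on-medication taper events out of the tables.

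**Share of dosing time outside the window, per discontinuer.** For termination on day d with a full taper, exposure by the SAP formula is d + 8 days and the early termination clause covers d days. The share outside is 8/(d + 8):

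- d = 7: 8/15 = 53%
- d = 14: 8/22 = 36%
- d = 21: 8/29 = 28%
- d = 50: 8/58 = 14%
- d = 104: 8/112 = 7%

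These termination days are illustrative. The documents give no dropout timing.

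**Per arm.** The documents give no dropout rate. I assume 2 to 9 early discontinuers per arm, which is 2/45 = 4% to 9/45 = 20% of the protocol's planned 45. On-medication days outside the window are then 2 × 8 = 16 to 9 × 8 = 72 per arm if all of them taper in full. Counting calendar days to Visit 13 gives 2 × 14 = 28 to 9 × 14 = 126, but 6 of each 14 days are off medication, so 16 to 72 is the relevant range.

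**The case against.** The strongest objection is SAP 6.9. It restricts safety summaries to T+M, and if it governs, taper events are left out for completers too and no asymmetry exists. That stands. The difference between completers and discontinuers holds only if 6.4.1.2 prevails over 6.9 and the early termination clause prevails over the general rule in its own cell. The omission of on-medication taper events survives under 6.9, but for everyone.

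Four further limits also stand:

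- Eight days is the default and the maximum. A subject who stops immediately under Protocol 4.5 loses no on-medication days.
- Only onsets after the early termination visit are affected. The event that led to stopping normally starts earlier and is already inside the window.
- The tables count subjects. A repeat of a preferred term already counted adds nothing unless it is the subject's first serious or related episode, or a more severe one.
- The overview table in SAP 6.4.1.1 (treatment-emergent, serious, related, leading to discontinuation, deaths) and the tables of events of special interest name no window.

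A reader might infer that these events survive only in listings. The documents do not support that, because the overview table could include them. A reader might also infer that events are undercounted selectively on ZX008. The clause is the same in both arms, and nothing in the documents gives a dropout rate, timing or imbalance, so neither size nor direction follows. Nor do the documents show that the cut is without any possible justification. Taper involves no crossover, but Protocol 4.8 lets some early discontinuers enter the extension case by case, so taper cannot be assumed for all of them.

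**Conclusion.** The concern holds as an inconsistency with a concrete consequence. SAP 6.1.6 contradicts itself on when the Double-Blind Treatment Period ends, and 6.4.1.2 and 6.9 name different windows for the safety tables. Under the early termination clause, treatment-emergent events with onset in up to 8 days of tapering fall outside the by-arm tables of 6.4.1.2 for discontinuers, while completers' taper events are counted. Under 6.9, both groups' taper events are left out. In either case the adverse event window is shorter than the exposure window of 6.2.4.1 for a tapered discontinuer.

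The size is 8 on-medication days per discontinuer who tapers in full, or 16 to 72 days per arm at an assumed 2 to 9 such subjects. No effect on the difference between arms can be claimed without dropout data. The primary efficacy analysis is not touched.

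**What to change.** In SAP 6.1.6, delete the sentence that ends the period at the early termination visit. Deleting it is not enough, because the last-day-on-treatment rule and the 14-day content list would still disagree. Replace the end-date wording with one rule for every subject who tapers, completer or discontinuer: through Visit 13, or through the last dose if Visit 13 is missed. Then reconcile 6.1.6, 6.4.1.2 and 6.9 so that all three name one adverse event window, and state that window for the overview table in 6.4.1.1 as well.

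If the sponsor keeps T+M as the main window, add a by-arm table of treatment-emergent events in the Taper period, covering all tapered subjects under the same rule.

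The cost is a few sentences of SAP wording and the programming of a period flag, plus one table if T+M is kept. Adverse events are already collected to Visit 13, and no dose, visit or clinical rule changes. The downside is that adverse event counts in the summaries may rise slightly.
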